2. Determine if intra-articular Triamcinolone therapy improves levels of a panel of inflammatory (cytokine), meniscus and cartilage metabolism and oxidative stress biomarkers as measured in synovial fluid from patients at relatively short-term time points after ACL injury (1-7 days, 10-17 days after injury and at time of surgery). Biomarkers to be tested include IL-1 α , IL-1 β , Collagen type I (NtxI) and collagen type II (CTXII) breakdown products, cartilage oligomeric protein (COMP) and glycosaminoglycan (GAG) and Xanthine Oxidase. Additionally, the change in IL-1 α and IL-1 β levels in the Triamcinolone treated and placebo individuals will be evaluated specifically for association with pain and function outcomes.

RESEARCH OBJECTIVES OF EXTENDED FOLLOW-UP SUB-STUDY:

1. Determine if joint health as evaluated by MRI at 24 months following ACL injury is influenced by the initial treatment with Kenalog. Two years following ACL injury MRI analysis using standardized T2-mapping will be performed on 10 control subjects and 10 subjects who have received Kenalog injections.

INVESTIGATIONAL PLAN

Description of Overall Study Design and Plan (See Figure 1 for study timeline)

This study is a multicenter, randomized, placebo controlled, double blinded, clinical trial. This trial will enroll 68 subjects between the ages of 14 and 33. This trial will be conducted at two clinical centers, the University of Kentucky and Vanderbilt University, as well as established criteria and support of the Multicenter Orthopaedic Outcome Network (MOON). A sub-study involving extended follow-up of patients, 24 months post-surgery will occur at the University of Kentucky clinical center only. This sub-study will involve 20 subjects of the initial University of Kentucky cohort returning for one additional follow-up MRI.

Description of observations and measurements to be made in this study:

[figure not shown]

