All biomarker analyses in synovial fluid will be performed by co-Investigator [name] (Duke University).

A portion of previously collected samples will be de-identified and shipped on dry ice to Children's National Medical Center at George Washington University where they will undergo the SOMAscan™ assay. The latest version of the SOMAscan assay measures 1,129 protein analytes in only 150 µl of serum. The assay offers exceptional dynamic range, quantifying proteins that span over 8 logs in abundance (from femtomolar to micromolar), with low limits of detection (38 fMol media LOD) and excellent reproducibility (5.1% median %CV) (<http://www.somalologic.com/Technology/SOMAscan-basic-info.aspx>). Once the analyses are complete any remaining samples at National Medical Center will be destroyed. At no time will anyone at Children's National Medical Center have access to subject identifiers or any other subject data.

Randomization: Patients will be randomized into one of four groups, and there will be 17 subjects per group.

- Group 1: will receive injection of Triamcinolone (40 mg) at time point 1 (1-2 days post injury) and saline placebo at timepoint 2 (12-14 post injury).
- Group 2: will receive a saline placebo injection at time point 1 (1-2 days post injury) and 40 mg Triamcinolone at time point 2 (12-14 days post injury.)
- Group 3: will receive two consecutive injections of 40 mg Triamcinolone, the first at time point 1 and the second at time point 2.
- Group 4 (control group): will receive two consecutive injections of saline placebo. The first at time point 1 and the second at time point 2.

Duration of Patient Enrollment: All subjects enrolled in the study will be followed for six months. Those subjects enrolled at the University of Kentucky site will be followed for 24 months, and 20 subjects from the main study will be recruited and enrolled in the extended follow-up MRI sub-study.

Duration of Study: Study duration will be 36 months from the commencement date. This duration may be extended to reach desired enrollment.

Data Safety and Monitoring Board (DSMB) - A DSMB consisting of 5 individuals (will monitor the study semi-annually and review reportable adverse events to the FDA as well as Vanderbilt and University of Kentucky Institutional Review Boards (IRBs). One of these members will maintain the allocation strategy, available upon request from the DSMB.

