The power calculations include several caveats. The power calculation was performed based upon the use of a IL-1 receptor antagonist. There is no clinical data available in a young patient population with knee ligament injuries regarding their pain improvement after cortisone injection. The IL1RA data is the most comparable. Cortisone is a wider spectrum anti-inflammatory than IL-1RA and thus may have a larger effect on pain control that may be longer lasting. In that case our study may be over-powered. First, for purposes of power calculation, we have not assumed a full repeated measures analysis, but have instead analyzed change from baseline at a single time point. Second, we note that in trials such as this, the power of a non-parametric analysis is never much lower than its parametric analog (the "asymptotic relative efficiency" of the Wilcoxon test is at least 0.95), leading us to conclude that our parametrically based power calculations should apply with equal force to a non-parametric analysis.

Statistical analyses - Results from a sample of this size may not be normally distributed. Therefore, non-parametric statistical measures may be used. Primary outcome measures evaluating for change in KOOS and IKDC will be assessed at multiple points and will be analyzed for change between groups using Friedman two-way ANOVA for repeated measures. Synovial fluid analyses comparing the three groups at three time points will be analyzed using the Wilcoxon Signed Rank Sum Test with Hochberg corrections for multiple time points. Alternatively, if results are normally distributed or can be transformed (e.g., by log transformation) to meet the criteria for normality for parametric analysis, then repeated measures ANOVA will be utilized comparing treatment groups. P-values of less than or equal to 0.05 will be considered statistically significant. For those subjects enrolled in the extended follow-up sub-study the 24 month time point will be examined as an additional time point. Additionally, correlation analyses will be used to examine the relationship between biomarkers collected at Visits 1-3 and KOOS and IKDC values and MRI findings at 24 month follow-up.

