Minimization of bias: Due to the randomized study design and the blinding of the investigator and patient to the drug used, we hope to eliminate any investigator or subject bias. Using broad and previously established enrollment criteria we hope to reduce selection bias to a minimum while protecting potentially vulnerable individuals through the exclusion criteria. Procedural bias and measurement bias will be reduced by the multicenter design and the blinded data analysis.

[figure not shown]
STUDY MEDICATION:

Formulation, Packaging and Labeling:

Kenalog® is a sterile suspension containing 40 mg/mL of micronized triamcinolone acetonide in the following inactive ingredients:

Polysorbate 80	0.20% w/v
Sorbitol Solution USP	50.00% w/v
Water for Injection qs ad	100.00% V
Hydrochloric Acid and Sodium Hydroxide, if required, to adjust pH to	4.0-8.0
Preservative: Benzyl Alcohol	0.90% w/v

The chemical name for triamcinolone acetonide is 9 α -Fluoro-11 β ,16 α , 17,21- tetrahydroypregna-1,4-diene-3, 20-dione cyclic 16, 17-acetal with acetone. Its structural formula is:

CLINICAL PHARMACOLOGY

Glucocorticoids, naturally occurring and synthetic, are adrenocortical steroids that are readily absorbed from the gastrointestinal tract.

Naturally occurring glucocorticoids (hydrocortisone and cortisone), which also have salt-retaining properties, are used as replacement therapy in adrenocortical deficiency states.

Their synthetic analogs are primarily used for their anti-inflammatory effects in disorders of many organ systems. When injected intraarticularly, triamcinolone acetonide can be expected to be absorbed slowly from the injection site.

Shipping, Storage, Handling: Unblinded study drug will be shipped from the manufacturer directly to the site. The syringes with Kenalog will be prepared at the site after study participants have been identified and consented and randomization has been performed. An unblinded nurse, nursing assistant or athletic trainer that has no primary involvement with this study will prepare a 10cc syringe with 40mg of Kenalog and 9cc of saline solution in standard aseptic technique. The syringe will be fitted with an opaque sleeve that does not allow for the visual distinction between study drug and placebo.

The study drug will be kept at the research site at The University of Kentucky (or Vanderbilt University respectively) and stored at controlled room temperature, 20°-25°C (68°-77°F), avoiding freezing and protected from light.

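### The plan states no stratification by centre and no centre term in any analysis, although its 24-month and MRI data come from Kentucky alone

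*Combined protocol and SAP*

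**What the plan says.** References are to the last protocol text in the combined file, the one with a mailed Visit 7 and a separate MRI Visit 8.

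- **Centres and size** (Description of Overall Study Design and Plan): "This trial will be conducted at two clinical centers, the University of Kentucky and Vanderbilt University" and "This trial will enroll 68 subjects between the ages of 14 and 33". The number per centre is not given.
- **Allocation** (Randomization): "Patients will be randomized into one of four groups, and there will be 17 subjects per group". No method, block size or stratification factor appears there or under Visit 1. On who holds the allocation, the Data Safety and Monitoring Board paragraph says "One of these members will maintain the allocation strategy, available upon request from the DSMB". The strategy is not described.
- **24 months** (Duration of Patient Enrollment): "Those subjects enrolled at the University of Kentucky site will be followed for 24 months".
- **MRI** (Description of Overall Study Design and Plan): "This sub-study will involve 20 subjects of the initial University of Kentucky cohort returning for one additional follow-up MRI". The sub-study objective fixes the split at 10 controls and 10 Kenalog recipients.
- **Analysis** (Statistical analyses): a Friedman test for KOOS and IKDC, a Wilcoxon signed-rank test for synovial fluid markers, correlations and, if normality holds, "repeated measures ANOVA will be utilized comparing treatment groups". Centre appears in none of them.
- **Bias** (Minimization of bias): "Procedural bias and measurement bias will be reduced by the multicenter design and the blinded data analysis".

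**The concern.** The plan counts having two centres as a protection against bias but describes no step that turns it into one. Two consequences follow if allocation is in fact unstratified.

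First, fixing 17 per arm overall does not fix the arm sizes within Kentucky. The 24-month questionnaire comparison, and the pool from which the MRI controls are drawn, then depend on how the arms happened to fall across centres.

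Second, in the pooled comparisons to 6 months, if subjects at one centre improve more than at the other, that difference stays in the residual variance unless the model contains centre.

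**Working it through.** **Inputs.** From the plan: 68 subjects, 17 per arm, 10 MRI controls, alpha 0.05, and a pilot effect size of 0.62 for change in KOOS pain. Assumed: the number at Kentucky, K (34, 40, 48 or 50); the centre difference in change, D, in SD units (0.3, 0.5, 0.8); two-sided tests.

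**The plan's own figure.** Sample Size and Power Analysis claims 80% power at effect 0.62 with 17 per group. A two-sided two-sample t test of 17 versus 17 gives 41.8%. That gap is separate from the centre question; 41.8% is used as the starting value below.

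**Kentucky arm sizes if allocation is unstratified.** With 17 controls among 68 and K subjects at Kentucky, the number of Kentucky controls is hypergeometric(68, 17, K), with mean K/4.

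| K | Expected controls | 95% range | P(fewer than 10) | P(largest and smallest arm differ by 5 or more) |
|---|---|---|---|---|
| 34 | 8.5 | 5 to 12 | 0.71 | 0.41 |
| 40 | 10 | 7 to 13 | 0.39 | 0.40 |
| 48 | 12 | 9 to 15 | 0.06 | 0.33 |
| 50 | 12.5 | 9 to 15 | 0.03 | 0.30 |

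**The same with centre-specific blocks of four.** At K = 40 there are exactly 10 controls. With mixed blocks of 4 and 8, subject 40 can fall halfway through a block of 8, giving 9 + (0 to 2) = 9 to 11. At K = 34 there are 8 or 9, so a shortfall is certain. Stratifying therefore helps only from about K = 40 upward, and only if the controls attend.

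**What unequal arms cost at 24 months.** Arms of 8 and 13 have an effective size of 2 × 8 × 13 / 21 = 9.9 per arm, against 10.5 if equal, a loss of about 6%.

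**Pooled comparisons to 6 months.** With Kentucky share s, omitting centre multiplies the variance of change by 1 + s(1 − s)D².

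| D | Variance factor, s = 0.5 | Power at 0.62, s = 0.5 | Power at 0.62, s = 50/68 |
|---|---|---|---|
| 0 | 1.000 | 41.8% | 41.8% |
| 0.3 | 1.0225 | 41.1% | 41.2% |
| 0.5 | 1.0625 | 39.8% | 40.2% |
| 0.8 | 1.160 | 37.0% | 38.0% |

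The loss is 41.8 − 41.2 = 0.6 to 41.8 − 37.0 = 4.8 points. A centre term recovers approximately that amount. If centre does not matter, the term takes one degree of freedom (32 to 31), and power goes from 41.82% to 41.76%, a cost of about 0.1 point.

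**The case against.** Much of the case on the other side stands, and it limits the point.

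- A reader might infer that allocation ignores centre. The documents do not show that. A DSMB member holds an undescribed strategy, which may be stratified, and Figure 1 is not reproduced. Every allocation probability above is conditional on unstratified allocation.
- A reader might infer that the MRI arm sizes are left to chance. They are set at 10 and 10. Chance affects only whether Kentucky can supply 10 controls and which active groups supply the Kenalog ten.
- A reader might infer that any centre difference in scores inflates the error. The primary outcome is change, and the Friedman and signed-rank tests work within subject, so a constant centre shift cancels. Only a difference in change matters, and a Kentucky-only comparison contains none.
- Chance imbalance in centre mix might be listed as an additional bias. Under randomization it is random error, and it is the route by which centre adds variance; counting both counts one effect twice.
- The bias sentence is about bias, not variance. Synovial markers are assigned to one co-investigator, KOOS is self-reported and the 24-month forms are mailed, so centre-specific measurement is limited. That is fair, but none of these protections comes from having two centres.
- A centre factor cannot simply be added to the named rank tests. This is correct, and the fix allows for it.

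**Conclusion.** The point holds as an inexpensive improvement, not as a flaw that invalidates the trial. No stratification by centre is stated and no analysis includes centre, while the 24-month questionnaires and the MRI sub-study rest on Kentucky subjects.

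If allocation is unstratified, the chance that Kentucky has fewer than 10 controls is 39% with 40 subjects there and 3% with 50. Kentucky's total enrolment drives this risk as much as the allocation method does, and at 34 stratification would not cure it. The power cost in the pooled comparisons is about 1 to 5 points at effect 0.62, for an assumed centre difference in change of 0.3 to 0.8 SD. The documents give neither the Kentucky share nor the centre difference.

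The 24-month population is also inconsistent. Research objective 1 lists 24 months for patients generally, Duration of Patient Enrollment limits it to Kentucky, and Statistical analyses ties that time point to the sub-study subjects.

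**What to change.** 1. **Analysis.** Add centre as a fixed factor in the pooled between-arm KOOS, IKDC and marker models. Where a rank method is kept, compare arms on change scores with a centre-stratified rank test (van Elteren), because the Friedman and signed-rank tests cannot carry a centre term. Cost: one degree of freedom and a change of named test, not just of wording. It also applies to subjects already allocated.
2. **Allocation.** State the method. If enrolment is still open and the list is not already stratified, allocate the remaining subjects from concealed, centre-specific permuted-block lists. Cost: overall arm totals may depart slightly from exactly 17. It secures 10 controls only if Kentucky enrols about 40 or more.
3. **Minimization of bias.** Credit the reduction in bias to the blinded analysis and drop the multicentre design from that sentence; the reference to blinding should stay.
4. **24-month population.** Reconcile research objective 1, Duration of Patient Enrollment and Statistical analyses on who is analysed at 24 months.

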Appendix A: Study Flow Chart

	Study Drug Treatment		Surgery ^s	Follow-up				Extended Follow-up Sub-Study
	Screening Baseline 1-2 days post injury (+/- 4 days)	12-14 days post injury		1-2 Weeks post surgery	4-6 weeks post surgery	6 Months Follow-up/Early Termination Visit	24 Months (+/-3) post surgery	24 Months (+/-3) post surgery
Study Time points	Time point 1	Time point 2						
Procedures	Visit 1	Visit 2	Visit 3	Visit 4	Visit 5	Visit 6	Visit 7 (out of office)	Visit 8 (MRI)
Informed Consent	X							X
Partial Medical History	X						X	
Medication History	X	X	X	X	X	X	X	
Smoking Status	X							
BMI Measurement	X							
Demographics	X							

X-Ray ¹	X							
MRI ^{2,6}	X							X
Range of Motion	X							
Knee Aspiration	X	X	X ^{3&5}	X ^{3&5}				
Randomization	X							
Study Medication	X	X						
Laboratory Tests								
Urine	X	X	X					
Blood	X	X	X					
Questionnaires And Scales								
Likert Pain Scale ⁴	X	X	X	X	X		X	
CSQ	X	X	X	X	X		X	
KOOS	X	X	X	X	X		X	X
IKDC	X	X	X	X	X		X	X
SF 36	X	X	X	X	X		X	
Catastrophizing Scale	X	X	X	X	X		X	
MARX Activity Scale								X

1 – All subjects must have standardized Flexion weight bearing x-rays. *Documentation of closed growth plates at screening will be noted on the routine SOC x-rays.*

2 - All subjects enrolled will have an MRI performed as a routine diagnostic tool regardless if surgery is to be scheduled or not. However, randomization can be performed prior to MRI as

the MRI examination is not necessary or required to diagnose the ACL tear.

3 – Knee aspiration will only be performed if the subject has –post-op fluid on the knee. Should a subject be enrolled into the study and choose not to undergo ACL reconstruction aspiration at time of surgery will be omitted.

4 - All subjects enrolled into the study must have been diagnosed with an ACL tear.

5 - Should a subject be enrolled into the study and choose not to undergo ACL reconstruction, subject will received treatment according to this protocol

6- Subjects enrolled in the extended follow-up sub-study will undergo a research specific MRI, that is not considered standard of care.

References:

